7.3.3 Expectedness

The PI, [name], will be responsible for determining whether an AE is expected or unexpected. An AE will be considered unexpected if the nature, severity, or frequency of the event is not consistent with the risk information previously described for the study agent.

7.4 Time Period and Frequency for Event Assessment and Follow-Up

The occurrence of an AE or SAE may come to the attention of study personnel during study visits and interviews of a study participant presenting for medical care, or upon review by a study monitor. All AEs including local and systemic reactions not meeting the criteria for SAEs will be captured on the appropriate RF. Information to be collected includes event description, time of onset, clinician's assessment of severity, relationship to study product (assessed only by those with the training and authority to make a diagnosis), and time of resolution/stabilization of the event. All AEs occurring while on study must be documented appropriately regardless of relationship. All AEs will be followed to adequate resolution.

Any medical condition that is present at the time that the participant is screened will be considered as baseline and not reported as an AE. However, if the study participant's condition deteriorates at any time during the study, it will be recorded as an AE. UPs will be recorded in the data collection system throughout the study.

Changes in the severity of an AE will be documented to allow an assessment of the duration of the event at each level of severity to be performed. AEs characterized as intermittent require documentation of onset and duration of each episode.

The PI will record all reportable events with start dates occurring any time after informed consent is obtained until 7 (for non-serious AEs) or 30 days (for SAEs) after the last day of study participation. At each study visit, the investigator will inquire about the occurrence of AE/SAEs since the last visit. Events will be followed for outcome information until resolution or stabilization.

All unresolved adverse events should be followed by the investigator until the events are resolved, the subject is lost to follow-up, or the adverse event is otherwise explained. At the last scheduled visit, the investigator should instruct each subject to report any subsequent event(s) that the subject, or the subject's personal physician, believes might reasonably be related to participation in this study. The investigator should notify the study sponsor of any death or adverse event occurring at any time after a subject has discontinued or terminated study participation that may reasonably be related to this study. The sponsor should also be notified if the investigator should become aware of the development of cancer or of a congenital anomaly in a subsequently conceived offspring of a subject that has participated in this study.

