Endpoint	Primary Endpoint: Opioid utilization for the first 72 hours after surgery, including during surgery, calculated as morphine equivalent. Secondary Endpoints: Opioid consumption Post-operatively Patient reported VAS scores in PACU Length of stay in PACU Patient reported VAS scores on POD 1, POD 2, POD 3, POD 7 Reaction to IPACK block Incidence of postoperative complications
Study Duration	The study will continue until 50 subjects are enrolled per arm, to allow for potential dropout and increased power.
Participant Duration	Each participant will be enrolled on DOS and complete their final follow up on postoperative day seven.
Duration of IP administration	Once during surgery
Population	50 patients per study arm scheduled for ACLR with BPTB autograft
Study Sites	NYU Langone Orthopedic Hospital and NYU Ambulatory Surgery Center at 38 th street
Number of participants	100
Description of Study Agent/Procedure	Patients in both the study and control group will receive the standard of care adductor canal block composed of 15 mL of Bupivacaine (0.25%). Patients in the study group will receive the additional IPACK block performed using 20 mL of Bupivacaine (0.25%) injected into the interspace between the popliteal artery and capsule of the knee. Patients will be blinded to their group allocation.
Reference Therapy	Reference is isolated adductor canal block
Key Procedures	Adductor canal block 15 mL 0.25% Bupivacaine, IPACK block with 20 mL 0.25% bupivacaine

CONFIDENTIAL

This material is the property of the NYU School of Medicine and Langone Medical Center. Do not disclose or use except as authorized in writing by the study sponsor

Statistical Analysis	Continuous and categorical baseline characteristics will be compared using Hedges standardized difference. Normally distributed data will be compared using t tests while non-normally distributed continuous outcomes will be assessed using the Mann-Whitney U test.
----------------------	--

CONFIDENTIAL

This material is the property of the NYU School of Medicine and Langone Medical Center. Do not disclose or use except as authorized in writing by the study sponsor

1 Background and Specific Aims

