3.4 Recruitment and Consent

Surgeon will identify potential subjects during their initial preoperative visit at which the surgeon will discuss the study with the patient. Should the potential subjects agree, the surgeon will provide the researcher with the name and medical record number of the patient. Researchers will receive the name and MRN of potential subjects identified by treating physician (study team members not volunteers) will utilize EPIC to extract patient demographic and surgical information to determine study eligibility. Once eligibility is confirmed, the treating physicians (TPs) will be notified via email, and they will discuss the study with the patient in the clinic at least 1 day prior to surgery to allow potential subjects to review and consider participation in the study.

If a subject requests information regarding opting out of further recruitment for all research, subjects will be directed to contact study coordinator or have subjects contact [contact] or [name].

CONFIDENTIAL

This material is the property of the NYU School of Medicine and Langone Medical Center. Do not disclose or use except as authorized in writing by the study sponsor

Written consent will then be obtained on the day of surgery in the preoperative holding area by an authorized research team member or the treating physician (surgeon or anesthesiologist). Once the patient is enrolled, they will be assigned a subject ID number and be randomized into a treatment group.

Once enrolled in the study, subject medical records will be accessed once more after surgery (for the second and final time) using subject MRNs by authorized study team members to collect demographic data including age, BMI, sex, smoking history, past surgical history, intraoperative findings, and opioid consumption (mgs) in the PACU. Once collected, deidentified data will be stored in the MCIT-managed HIPAA-compliant and encrypted version of Redcap in addition to the MCIT governed, firewall protected shared drive located on the NYU MCIT network.

Data linking protected health information to the deidentified patient record number will be kept in a local password-protected computer. Only the principal investigator will have access to the identified data.

Process of Consent

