3.5 Duration of Study Participation

The study will remain open until 50 patients are recruited for each intervention arm of the study. The actual subject participation length will be seven days.

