4.2.3 Follow-Up Phone call/message (POD 1, POD 2 and POD 3)

Phone call to patient to collect additional data on opioid use following discharge, on POD 1, POD 2 and 3 after surgery

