4.2.4 Postoperative Visits

Patients will present to postoperative visit #1 of POD 7 per standard of care, at which point VAS pain, ROM, and strength will be assessed.

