4.2.5 Withdrawal/Early Termination Visit

Subjects may discontinue their participation in the study at any time. As there is only a single intervention, and the safety of this is not in question, further follow up will not be required if a subject decides to terminate their participation in the study.

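### SAEs are to be recorded for 30 days after participation, but the visit schedule has no safety check after POD 7 and the last day of participation is not consistently defined

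*Combined protocol and SAP*

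**What the plan says.** **Recording window.** Section 7.4 starts recording at consent and runs it "until 7 (for non-serious AEs) or 30 days (for SAEs) after the last day of study participation". It asks for all AEs on study to be documented irrespective of causality and followed until they resolve. It places active questioning at visits: "At each study visit, the investigator will inquire about the occurrence of AE/SAEs since the last visit".

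**Length of participation.** Section 3.5: "The actual subject participation length will be seven days". The Protocol Summary has each participant "complete their final follow up on postoperative day seven". Section 6.2, however, lists functional outcomes at 6 months, including strength and range of motion, as a secondary endpoint.

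**Scheduled contacts.** Section 4.2.3 gives the POD 1 to 3 contacts an opioid-use purpose: "Phone call to patient to collect additional data on opioid use following discharge". The last visit is in section 4.2.4: "Patients will present to postoperative visit #1 of POD 7 per standard of care". Section 4.2 lists nothing later, and the 6-month assessment does not appear there.

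**Chart access.** Section 3.4: "subject medical records will be accessed once more after surgery (for the second and final time". No date is given. The items listed for collection are demographics, history, intraoperative findings and PACU opioid use. Adverse events are not among them.

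**Withdrawal.** Section 4.2.5: "further follow up will not be required if a subject decides to terminate their participation in the study". The reason given is that the intervention is single and its safety is not in doubt.

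**The concern.** The plan promises a safety window longer than its scheduled means of observing it. Between the last scheduled visit and the end of the SAE window, no one is assigned to ask the subject or look in the chart. The wording on chart access, read literally, rules out looking later. A subject who leaves with an open AE falls under two instructions that pull apart: section 7.4 follows the event to resolution, and section 4.2.5 requires no further follow-up.

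Two uses of the data depend on complete counts. Section 7.6 compares SAE rates between arms by chi-square at p<0.01 and can suspend accrual on the result. The Protocol Summary lists the incidence of postoperative complications as a secondary endpoint. Section 5.1 names nerve injury and injection-site infection among the risks, and section 7.6 puts injection-site infection under three-monthly review.

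**Working it through.** The plan states no figure for coverage of the window, so there is none to reproduce. The check is day arithmetic on its own numbers.

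**Inputs.** Last day of participation: POD 7 (Protocol Summary, section 3.5). Window after that day: 30 days for SAEs, 7 for non-serious AEs (section 7.4). Last scheduled visit: POD 7 (section 4.2.4).

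**Formula.** Window end = last participation day + window. Share without scheduled ascertainment = days after the last visit / days from surgery to window end.

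- SAEs: 7 + 30 = POD 37; 30/37 = 81%.
- Non-serious AEs: 7 + 7 = POD 14; 7/14 = 50%.
- Counting the day of surgery as a day: 30/38 = 79% and 7/15 = 47%.

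Days up to POD 7 count as covered because the POD 7 visit asks about events since the previous visit.

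**Withdrawal**, assuming the day of withdrawal is the last day of participation. The share of the SAE window with no required contact is:

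- withdrawal on day 0: 30/30 = 100%
- withdrawal on day 1: 30/31 = 97%
- withdrawal on day 3: 30/33 = 91%

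**If the 6-month assessment in section 6.2 counts as participation**, assuming it falls on day 180 to 183:

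- SAE window end: 180 + 30 = day 210, to 183 + 30 = day 213.
- Gap from POD 7 to that assessment: 180 − 7 = 173 days, to 183 − 7 = 176 days.
- A further 30 days after it have no scheduled contact.

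The window therefore closes on POD 37 or at about day 210 to 213, depending on which section is followed.

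**Sensitivity of the section 7.6 rule to a missed event.** This is an illustration, not a forecast. Take 50 subjects per arm, k SAEs in one arm and 0 in the other. The uncorrected statistic is 100k/(100 − k). With continuity correction it is 100(k − 1)²/[k(100 − k)].

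| k v 0 | Uncorrected | Corrected |
|---|---|---|
| 6 | 600/94 = 6.38, p = 0.0115 | 2500/564 = 4.43, p = 0.035 |
| 7 | 700/93 = 7.53, p = 0.006 | 3600/651 = 5.53, p = 0.019 |
| 8 | 800/92 = 8.70, p = 0.003 | 4900/736 = 6.66, p = 0.0099 |

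The p<0.01 threshold is crossed at 7 events uncorrected and at 8 corrected. Near the threshold, one unrecorded SAE changes the result. Section 7.6 itself calls SAEs rare, so counts this high are not expected.

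**The case against.** A reader might infer that most of the SAE window is unobserved. The documents do not support that. Section 7.4 names presentation for medical care and monitor review as ways events come to light. It has subjects told at the last scheduled visit to report later events that they or their physician believe related, and it asks for sponsor notification of possibly related events at any time after discontinuation. Sections 8 and 10.3 allow monitors to inspect medical records. The right description is that events are not actively ascertained. What remains is that these routes are passive. The self-report instruction covers only events thought to be related, although section 7.4 wants all of them. It is also given at a visit that a withdrawn subject may not attend.

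A reader might also infer that all contact ends at POD 7, or that the passages cannot all be followed. Neither is established. If the 6-month assessment is a study visit, it would ask about events since POD 7, though late and by recall. The chart access in section 3.4 is undated and could fall after POD 37, though nothing says that it will. Section 4.2.5 says follow-up is not required, which does not forbid it, and its waiver concerns subjects who choose to leave. Termination by the investigator for an AE is a separate route in section 3.7. A recording window that outlasts the last visit is not in itself a contradiction.

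The consequences are also limited. The stopping rule in section 7.6 names neurotoxicity, cardiotoxicity and allergic reaction to bupivacaine. Section 5.1 places monitoring for neurologic and cardiac toxicity at the block, with monitoring for adverse effects continuing in the PACU, so the named events are mainly expected in the observed period. The complications endpoint has no stated time window. Both arms have the same follow-up. These points stand, and they reduce the size of the problem without closing the gap.

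**Conclusion.** The point holds as a gap in scheduled safety ascertainment together with wording that needs reconciling. If participation ends at POD 7, nothing in the schedule looks for SAEs on POD 8 to 37 (30 of 37 days) or for non-serious AEs on POD 8 to 14 (7 of 14 days). The literal text of section 3.4 bars a further chart review, and section 4.2.5 is in tension with following AEs to resolution under section 7.4. Because section 6.2 conflicts with the Protocol Summary, section 3.5 and section 4.2, the end of the window is not defined.

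It would be wrong to read 81% as the share of SAEs missed. It is a share of days, and after a single injection the risk need not be even over 37 days. The documents give no figure for events after POD 7, and nothing in them shows that capture would differ between arms. Under-ascertainment could lower the counts used in section 7.6 and for the complications endpoint, by an amount that cannot be stated. This concerns completeness of safety data, not the validity of the primary endpoint.

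**What to change.** 1. Define the last day of study participation by reconciling the Protocol Summary, section 3.5, section 4.2 and the 6-month item in section 6.2.
2. Add one dated SAE question by email or phone, or one dated chart check, at the end of the stated window.
3. Amend the statement in section 3.4 that the post-surgery chart access is the final one, so that this check is allowed.
4. Reconcile section 4.2.5 with section 7.4 so that withdrawing subjects are asked for permission to record safety outcomes. Section 10.3 already seeks permission to collect vital status when authorization is revoked.

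Shortening the window to match the visits would remove the mismatch but would add no safety information.

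Cost: one brief check per subject, 100 in total, plus protocol and consent wording.

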7.5 Reporting Procedures - Notifying the IRB

7.5.1 Unanticipated Problem Reporting

Incidents or events that meet the OHRP criteria for UPs require the creation and completion of an UP report form. It is the site investigator's responsibility to report UPs to their IRB. The UP report will include the following information:

1. Protocol identifying information: protocol title and number, PI's name, and the IRB project number;
2. A detailed description of the event, incident, experience, or outcome;

CONFIDENTIAL

This material is the property of the NYU School of Medicine and Langone Medical Center. Do not disclose or use except as authorized in writing by the study sponsor

3. An explanation of the basis for determining that the event, incident, experience, or outcome represents an UP;
4. A description of any changes to the protocol or other corrective actions that have been taken or are proposed in response to the UP.

To satisfy the requirement for prompt reporting, UPs will be reported using the following timeline:

- UPs that are SAEs will be reported to the IRB within 7 days of the investigator becoming aware of the event.
- Any other UP will be reported to the IRB within 7 days of the investigator becoming aware of the problem.
- All UPs should be reported to appropriate institutional officials (as required by an institution's written reporting procedures), the supporting agency head (or designee), and OHRP within 7 days of the IR's receipt of the report of the problem from the investigator.

7.6 Safety Oversight

It is the responsibility of the Principal Investigator [name], and co-investigators [name] MD and [name] MD to oversee the safety of the study at his/her site. This safety monitoring will include careful assessment and appropriate reporting of adverse events as noted above, as well as the construction and implementation of a site data and safety-monitoring plan. Adverse Events such as development of an allergy to local anesthetic, inadvertent intravascular injection of local anesthetic and infection at site of injection will be reviewed every three months. Serious adverse events are rare and are unlikely to occur but if a serious adverse event occurs, steps will be taken to address it. Study recruitment will cease temporarily while a data safety monitoring team convenes to review the event. Medical monitoring will include a regular assessment of the number and type of serious adverse events.

Data Safety Monitoring Plan

The principal investigator [name], and co-investigators [name] MD and [name] MD are responsible for data safety and monitoring of the overall study.

The following data points and outcomes will be reviewed during data safety monitoring reviews: number of patients enrolled, pain scores of patients, AEs and SAEs such as neuro and cardiotoxicity. Data will be monitored quarterly and will be reported at the time of continuing review.

The stopping rules for the study are adverse harm to patients, as measured by the serious adverse events, specifically neurotoxicity, cardiotoxicity, or allergic reaction to bupivacaine. A chi-square test will be used to determine if there is a statistically significant difference ($p<0.01$) in the rate of SAEs between treatment arms. If there is a statistically significant difference in the rates of SAEs between arms, accrual to the trial will be suspended while the study team and data safety monitoring team conduct an evaluation of the events.

The PI will oversee all study activities including data collection and management and will ensure study personnel conduct this study based on the approved protocol.

8 Source Documents and Access to Source Data/Documents

Source data is all information, original records of clinical findings, observations, or other activities in a clinical trial necessary for the reconstruction and evaluation of the trial. Source data are contained in source documents. Examples of these original documents, and data records include: hospital records, clinical and

CONFIDENTIAL

This material is the property of the NYU School of Medicine and Langone Medical Center. Do not disclose or use except as authorized in writing by the study sponsor

office charts, laboratory notes, memoranda, subjects' diaries or evaluation checklists, pharmacy dispensing records, recorded data from automated instruments, copies or transcriptions certified after verification as being accurate and complete, microfiches, photographic negatives, microfilm or magnetic media, x-rays, subject files, and records kept at the pharmacy, at the laboratories, and at medico-technical departments involved in the clinical trial. It is acceptable to use CRFs as source documents. If this is the case, it should be stated in this section what data will be collected on CRFs and what data will be collected from other sources.

The study case report form (CRF) is the primary data collection instrument for the study. All data requested on the CRF must be recorded. All missing data must be explained. If a space on the CRF is left blank because the procedure was not done or the question was not asked, write "N/D". If the item is not applicable to the individual case, write "N/A". All entries should be printed legibly in black ink. If any entry error has been made, to correct such an error, draw a single straight line through the incorrect entry and enter the correct data above it. All such changes must be initialed and dated. DO NOT ERASE OR WHITE OUT ERRORS. For clarification of illegible or uncertain entries, print the clarification above the item, then initial and date it.

Access to study records and patient contact will be limited to IRB-approved study team members, not volunteers. The investigator will permit study-related monitoring, audits, and inspections by the IRB/EC, the sponsor, government regulatory bodies, and University compliance and quality assurance groups of all study related documents (e.g. source documents, regulatory documents, data collection instruments, study data etc.). The investigator will ensure the capability for inspections of applicable study-related facilities (e.g. pharmacy, diagnostic laboratory, etc.).

Participation as an investigator in this study implies acceptance of potential inspection by government regulatory authorities and applicable University compliance and quality assurance offices.

9 Quality Assurance and Quality Control

QC procedures will be implemented beginning with the data entry system and data QC checks that will be run on the database will be generated. Any missing data or data anomalies will be communicated to the site(s) for clarification/resolution.

Following written SOPs, the monitors will verify that the clinical trial is conducted and data are generated, documented (recorded), and reported in compliance with the protocol, GCP, and the applicable regulatory requirements.

10 Ethics/Protection of Human Subjects

